Depression	PHQ-4	Patient Health Questionnaire for depression and Anxiety (PHQ-4) includes four questions, scored on a 4-point Likert scale ranging from 0 ("not at all") to 3 "nearly every day). The questions are: 1. Depression (2 items from PHQ-9): Little interest or pleasure in doing things. Feeling down, depressed, or hopeless. Anxiety: (2 items from GAD7): Feeling nervous, anxious, or on edge. Not being able to stop or control worrying. Scoring: Each question is scored from 0-3, leading to a total score range of 0-12. The total score helps to classify the overall level of psychological distress: 0-2: Minimal or none, 3-5: mild, 6-8: Moderate, 9-12: Severe. ⁹⁷
Sense of coherence	SOC-13	The SOC-13 (Sense of Coherence-13) is a brief version of the Sense of Coherence scale developed by Aaron Antonovsky to assess an individual's ability to manage stress and maintain health. It measures three core dimensions: 1. Comprehensibility: The extent to which life is perceived as structured and understandable. 2. Manageability: The belief that one has the resources to cope with life's demands. 3. Meaningfulness: The degree to which life is seen as meaningful and worth engaging in. The SOC-13 contains 13 items scored on a 7-point Likert scale, with higher scores indicating a stronger sense of coherence and better stress resilience. ⁹⁸

Self-efficacy/self-management	PAM₁₃	The PAM ₁₃ (patient activation measure) is a 13-item survey, assesses an individual's knowledge, skill, and confidence for self-management. It categorizes patients into four levels based on their activation score, which ranges from a lack of understanding of the need for active participation in health (level one) to challenges in maintaining positive health behaviors over time (level four). The questionnaire consists of 13 questions, where each question is a statement. Respondents indicate on a scale from 1-4 how much they agree with the given statement (1 = strongly disagree, 2 = disagree, 3 = agree, 4 = strongly agree). All scores are then summed and divided by the number of answered questions, resulting in a score between 13-52. The score is then placed into one of four activity levels below, where level 1 is the lowest. ⁹⁹
Smoking status	Self-reported	Smoking status assessed as change from baseline. The number of participants successfully quitting smoking out of all active smokers

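### The PAM13 scoring rule in Table 1 yields a score from 1 to 4 and cannot produce the 13-52 range stated for it

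*Protocol*

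**What the plan says.** The scoring is set out in the PAM13 row of Table 1 (protocol section 7.2), in four consecutive statements:

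- Number of items: "The questionnaire consists of 13 questions, where each question is a statement".
- Item scores: "Respondents indicate on a scale from 1-4 how much they agree with the given statement".
- Rule and result: "All scores are then summed and divided by the number of answered questions, resulting in a score between 13-52".
- Use of the result: "The score is then placed into one of four activity levels below, where level 1 is the lowest".

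No cut-offs for the four levels follow in the text available. Table 2 schedules PAM13 at baseline, the day before surgery and 30 days after surgery. Section 2.2 says that the secondary outcomes are collected to describe levels, variation and change, which can inform the sample size of the later trial. Section 9.1 says that continuous variables will be summarised as mean and SD and that changes over time will be analysed by a repeated measurements method.

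**The concern.** The division turns the score into an average item response, yet the range given for it is that of a 13-item total. Both are in the same sentence, so anyone scoring the questionnaire must drop one or add a step that the sentence does not contain.

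Three things are at stake. First, two people working from the same text could report PAM13 on scales that differ 13-fold, and a published mean and SD could not be carried forward safely without knowing which scale was used. Second, the activation level is read off the score, and a value between 1 and 4 does not lie on a 13-52 scale. Because the levels are themselves numbered 1 to 4, a mean item score could even be mistaken for a level. Third, the obvious workaround, a plain sum that matches the stated range, drops the adjustment for unanswered items that the division appears intended to provide.

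**Working it through.** **Inputs**, all from the PAM13 row of Table 1: 13 items; minimum item score 1; maximum item score 4; rule = sum / number answered; stated range 13-52.

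**Reproducing the stated range.** Let m be the number of items answered, from 1 to 13.

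| Formula | Minimum | Maximum | Gives 13-52? |
|---|---|---|---|
| Sum / m (rule as written) | m x 1 / m = 1 | m x 4 / m = 4 | No, for any m |
| Plain sum, all 13 answered | 13 x 1 = 13 | 13 x 4 = 52 | Yes, but without the division |
| Plain sum, 11 answered | 11 x 1 = 11 | 11 x 4 = 44 | No |
| Sum / 13, all 13 answered | 13 / 13 = 1 | 52 / 13 = 4 | No |
| (Sum / m) x 13 | 1 x 13 = 13 | 4 x 13 = 52 | Yes, for any m |

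The rule as written does not reproduce 13-52. Only the last row keeps both the division by answered items and the stated range.

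**Effect of using one scale or the other.** Write X for the score on 13-52 and Y = X / 13 for the score on 1-4. Then mean(Y) = mean(X) / 13 and SD(Y) = SD(X) / 13. A standardised difference is (difference in means) / SD. Both parts are divided by 13, so the ratio is the same, and so are test statistics and p-values. Only the unstandardised figures change.

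**Effect of the plain-sum workaround when items are skipped.** If k items are skipped and the mean of the answered items is a, the plain sum is (13 - k) x a and the rescaled score is 13 x a. The shortfall is k x a, which is 1 to 4 points per skipped item. Example: 11 items answered, all with 3. Plain sum = 11 x 3 = 33. Rescaled score = (33 / 11) x 13 = 39. The shortfall is 6 points for that patient and, with 25 patients in a group (section 3.6), 6 / 25 = 0.24 points on the group mean. The number of skipped items is not known, so this is an illustration and not a prediction.

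**The case against.** The strongest reply accepts the arithmetic and disputes the consequences.

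- **A change of unit is not bias.** If the division is applied uniformly, every score is the 13-52 score divided by 13, and the inference does not change. This stands. A reader might infer that the PAM13 comparisons would be invalid; for the continuous score analysed on one scale, they would not be.
- **No misclassification is shown.** A reader might infer that patients will be assigned to wrong activation levels. The text gives no cut-offs, so this cannot be demonstrated or counted. What can be said is narrower: a score of 1-4 cannot be placed on levels defined on 13-52.
- **The document does not say which half is the slip.** Dropping the division, multiplying by 13, or keeping the mean and stating 1-4 would each remove the contradiction. This stands too. The instrument's own scoring rests on the Danish validation study cited as reference 99, which is not available here.
- **The loss from skipped items is conditional.** The protocol does not say that a plain sum will be used, and detailed handling of missing items may properly sit in the SAP. This is fair. The illustration is a reason to prefer one repair over another, not a defect in itself.
- **The place and the outcome are minor.** The sentence sits in a column that justifies the choice of instruments. PAM13 is one of many exploratory measures, and patient activation is not among the domains that section 9.1 names for the secondary aim. This limits the weight of the point. It does not excuse the sentence, because Table 1 does serve to describe scoring: the PHQ-4 row gives four items scored 0-3 and a total of 0-12, which is consistent (4 x 3 = 12).

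**Conclusion.** Wrong as written. The rule gives 1-4 for any number of answered items, and the stated result is 13-52. No other part of the protocol corrects this. The size is a factor of 13 in any reported mean, SD or change, plus a level assignment that cannot be carried out from the rule as it stands.

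The conclusion rests only on the item count, the item range and the rule, all of which the protocol states. It does not extend to a claim that particular levels are wrong, that tests would be biased, or that the range rather than the rule is the mistake. The feasibility outcomes, the feasibility criteria in sections 7.1 and 3.6's sample size of 25 per group do not depend on PAM13. This should be corrected before scoring, but it does not threaten the study's main purpose.

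**What to change.** Check the PAM13 sentence in Table 1 against the cited scoring source and make rule and range agree before any questionnaire is scored. Unless that source says otherwise, use the one formula compatible with both halves of the present sentence:

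PAM13 score = (sum of answered items / number of answered items) x 13, range 13-52.

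It equals the plain sum when the form is complete, and it avoids the downward shift that a plain sum gives when items are skipped. State it in Table 1, use the same formula in REDCap for electronic and paper forms alike, and assign the four levels from the score on that same scale, with the cut-offs given or referenced. If the source supports a different convention, state that one with its matching range.

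The cost is one sentence in Table 1 and one calculated field in REDCap. No data collection, visit or sample size changes.

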8.1 Data from questionnaires

The questionnaires are self-administrated and will be completed electronically in REDCap a web-based data capture tool¹⁰³ which meets the data legislation for logging. The study participant will receive an email with link to a website through which questionnaires can be completed. The e-mail contains a login and password for the trial participant's access. If patients do not complete the questionnaire electronically, the paper questionnaires will be handed out to the patient, and independent study personal then enters the responses into REDCap. Participants will complete the questionnaires at all three time points: baseline, the day before CABG surgery after the intervention, and 30 days post-surgery. The filled-out questionnaires typed in REDCap and responses will be stored in a secure folder with limited access ("lovbeskyttet mappe").

8.2 Data from patient records

Preoperative relevant information, including patient name and age as well as details about the patient's heart diagnosis and medical status (such as Euroscore II, LVEF, and NYHA class), will be reviewed from the patient record (SP) without consent by the responsible heart surgeon to inform the study about eligibility of patients referred to elective CABG surgery. Additionally, and with consent, postoperative complications, such as infections and arrhythmias, along with any adverse events occurring during the intervention period, will be documented from the patient record. Information on the length of stay (both ICU-LOS and overall, LOS) and the number of days alive out of the hospital within 30 days will be calculated using data from both the patient record and Danish registers. Data will be retrieved from the national electronic record system (E-journal) by an electronic healthcare software (Epic, Madison, WI, USA), which secures a complete enrolment and follow-up as the recording is a requirement for economic reimbursement. All data is processed and stored confidentially, and personal data will always be handled in accordance with the Danish Data Protection Act and the General Data Protection Regulation. Data are stored pseudo-anonymously in a separate approved and secure database (Capital Region REDCap), which only the doctors, research assistants and project nurses of the study will access using person-specific log-in and password. An anonymous trial number are used as patient identification in the REDCap database. The key linking the study-id with the personal id is kept separately from the study data with limited access controlled by the study investigator or designee. Authority and obligations are documented in the log of delegation of responsibility in the trial. The patient's records will be reviewed by study related personnel to assess clinical and safety endpoints. The informed consent gives the investigator and possibly control authority direct access to data from the patient's journal. These are used to view information on the participant's medical condition necessary for the conduct of the study and for self-control, quality control and monitoring. The patient is informed about this and gives informed consent to this when entering the study. If a potential participant declines to participate in the project, we will request permission to collect information regarding their age, gender and current medical status pertinent to their admission for CABG surgery and only if a written informed consent is obtained.

8.3 Data from Danish registries

A register-based follow-up after 30 days will be used to evaluate DAOH₃₀. The study will use data from the following registers: The National Patient Register and The Causes of Death Register.

8.4 Biological material

All blood analyses are a part of usual care and the routine blood work when meeting for surgery and will be performed according to clinical standards at the hospital and therefore a research biobank will not be established.

9. Analysis

9.1 Statistical methods

Data analysis will be limited to descriptive summary statistics of the proposed endpoints, and calculation of feasibility measures, enrollment rates and dropout rates within a period. The feasibility analysis will be based on the components of process, resources, management, and scientific approach.⁵⁸ Process: number of eligible patients for enrollment; Successful recruitment rate, rate of adherence to the interventions at each time point; Rate of loss to follow up; Rates of completed questionnaires; Understanding of the questionnaires. Resources: Time to screen and consent patients, Time to conduct baseline and follow-ups; Identification of any challenges related to randomization or data collection; Identification of potential barriers of the preoperative programme. Management: Identification of any challenges related to randomization or data collection; Identification of potential barriers for the intervention. Scientific approach: Estimates of improvement in patient-reported outcomes compared to usual care, patients' response to topics and content in the programme and identification of potentially patient safety issues. As recommended for the analysis of pilot studies⁵⁸ descriptive statistics will be presented as mean and standard deviations (SD) for continuous variables and frequencies and percentages for categorial variables at baseline and follow-ups. Collected data on patient characteristics will be presented in tables. Continuous variables will be displayed as mean (SD), while categorical variables will be presented as number (n) and percentage (%). Descriptive statistics will be used to answer the primary study parameter of feasibility. Feasibility will be presented in tables and based on participation rate (n, %), reasons for nonparticipation (n, %, text), adherence to the prehabilitation program (%), dropout rates (%), reasons for dropout (n, %, text), adverse events (n, %, text). The secondary aim is to evaluate the patients' responses over time in terms of physical activity, muscle strength, functional capacity, body composition, quality of life and symptoms of depression, and anxiety. A repeated measurements analysis will be used to analyze changes over time in continuous variables. *P*- values <0.05 will be considered statistically significant.

10. Ethics

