2.1 Primary objective

The primary objective of this feasibility study is to determine if it is feasible for patients awaiting elective CABG surgery to participate in a preoperative homebased multimodal prehabilitation intervention. We will evaluate this through completion of the following objectives:

- Assess the proportion of eligible patients that are recruited into the study.
- Assess the suitability of inclusion and exclusion criteria by examining recruitment data.
- Explore reasons for non-consent to study participation.
- Assess the acceptability of the study to patients by measuring recruitment and retention to the study and thorough qualitative interview responses.
- Assess the acceptability of the intervention through qualitative interviews and retention rates during the study.
- Assess adherence to and completion of the intervention (i.e. do participants adhere and work through all components of the intervention) and explore engagement and satisfaction with the interventions by qualitative interviews.
- Assess the proportion of patients lost to follow-up after study entry.
- Assess safety of the interventions.
- Explore the appropriateness of outcome measures, completion rates and assess response to questionnaires through qualitative interviews.
- Evaluate the logistics of delivering a home-based tele-exercise training intervention through qualitative interview responses from both health care professionals and patients.
- Determine the “prehabilitation window” (length of time between MDT-conference and CABG surgery)

2.2 Secondary objective:

The secondary objectives will evaluate if the multimodal prehabilitation intervention has an impact on preoperative and postoperative outcomes. For this we will collect data on study outcomes to assess levels, variation, and changes over time, which can inform sample size for the future RCT, as shown in **Table 1**, section 7.2.

3. Method

[figure not shown]

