3.1 Study design

The CABGpreHAB feasibility study is designed as a randomized pilot study, aiming to assess the feasibility of a multimodal prehabilitation intervention plus usual care versus usual care alone in patients awaiting elective CABG surgery. It is an investigator-initiated study designed as an open-label, single-center randomized controlled feasibility study (allocation ratio 1:1) with blinded outcome assessment, designed to assess the method proposed for use in a larger RCT. This protocol follows guidance from Standard Protocol Items: Recommendations for Interventional Trials (SPIRIT).⁶⁰ The CABGpreHAB study will be registered at www.ClinicalTrials.gov before initiation.

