3.4 Blinding

Due to the nature and conditions of prehabilitation, the interventions are open, making it impossible to blind the interventions to the staff and patients.⁶¹ However, all physical testing, data collection, and administration will be conducted by blinded staff. Statistical analysis of outcomes and the conclusions derived from these analyses will also be performed in a blinded manner. The study results will be analyzed by an independent statistician, and the research group will interpret the results. The conclusions will be prepared in two versions before the allocation code is broken, with each version assuming alternately that one arm is the intervention: one version will assume that arm A is the intervention, and the other will assume that arm B is the intervention.

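### Section 9.1 confines the analysis to description, then sets a p<0.05 rule on change over time, and nothing ties that rule to the between-arm difference that the impact objective in section 2.2 needs

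*Protocol*

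**What the plan says.** Three statements in Protocol section 9.1 bear on the point.

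- The opening sets the scope: "Data analysis will be limited to descriptive summary statistics of the proposed endpoints", together with the calculation of feasibility measures, enrolment and dropout.
- Further down, description is assigned to the primary question: "Descriptive statistics will be used to answer the primary study parameter of feasibility".
- The section ends with the secondary aim, worded as how patients respond over time and naming no comparator. The method is "A repeated measurements analysis will be used to analyze changes over time in continuous variables", and P-"values <0.05 will be considered statistically significant".

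Section 2.2 states the secondary objective as to "evaluate if the multimodal prehabilitation intervention has an impact on preoperative and postoperative outcomes". Its next sentence says that this will be done by looking at the level, spread and change of the outcomes, partly to inform the sample size of the later trial.

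Other text points to a comparison of arms. Section 3.1 describes the design as "multimodal prehabilitation intervention plus usual care versus usual care alone in patients awaiting elective CABG surgery". Section 3.4 says "The conclusions will be prepared in two versions before the allocation code is broken", with each arm in turn taken as the intervention, and section 11.4 repeats this. Within 9.1, the scientific-approach component lists "Estimates of improvement in patient-reported outcomes compared to usual care".

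Section 3.6 gives 25 patients per group and no power calculation. Sections 7 and 7.2 call the clinical outcomes explorative.

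**The concern.** There are two defects in the same section.

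First, an analysis limited to descriptive summaries cannot also contain a test judged at p<0.05. A statistician writing an analysis plan could not follow both statements.

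Second, the one inferential rule in the protocol is attached to change over time. Patients may change while they wait or after CABG in either arm, so a significant change does not show that prehabilitation did anything. The impact question in 2.2 needs the difference between randomised arms, and no sentence links the p-value to that difference.

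What is at stake is how the secondary results are reported and carried into the planning of the full-scale trial. Read one way, the rule invites a claim of impact from change that both arms share. Read the other way, it invites a claim of no impact from a study that was never sized to detect one.

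**Working it through.** **The protocol's own figure.** There is no power-based figure to reproduce. Section 3.6 takes 25 per group from pilot-size recommendations of 24 to 50; 2 × 25 = 50 lies within that range. The protocol gives no effect size, SD or correlation for any secondary outcome. All shifts, effects and correlations below are therefore assumptions, with complete data and two-sided 0.05 tests based on the noncentral t distribution.

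**Reading 1: the rule is applied to a pooled time effect.** Suppose there is no treatment effect and both arms shift equally by d, in SD of the change score. With n = 50 and 48 degrees of freedom, the noncentrality is d × √50.

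| Assumed equal shift d | Noncentrality | Chance of p<0.05 |
|---|---|---|
| 0.2 | 1.41 | 28% |
| 0.5 | 3.54 | 93% |
| 0.8 | 5.66 | >99% |

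None of these significant results would reflect an effect of prehabilitation.

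**Reading 2: the rule is applied to the arm difference.** Let d be the true difference in SD of the follow-up score. Unadjusted, the noncentrality is d / √(2/25) with 48 degrees of freedom. Adjusted for a baseline value with correlation r, it is d / √((2/25)(1 − r²)) with 47 degrees of freedom.

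| Assumed difference d | Power, unadjusted | Power, adjusted at r = 0.5 |
|---|---|---|
| 0.2 | 11% | 13% |
| 0.5 | 41% | 52% |
| 0.8 | 79% | 89% |

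**What an estimate would offer instead.** The unadjusted 95% confidence interval has half-width t(48) × √(2/25) = 2.011 × 0.283 = 0.57 SD. With baseline adjustment it is t(47) × √(2/25) × √(1 − r²):

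| Assumed r | Half-width (SD of follow-up score) |
|---|---|
| 0.3 | 0.54 |
| 0.5 | 0.49 |
| 0.6 | 0.46 |
| 0.7 | 0.41 |

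The interval is wide, but it shows how little the study can settle about impact. A significant or non-significant label hides that.

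**The case against.** **An arm comparison is clearly in view.** The design, the two-version conclusions and the phrase on patient-reported outcomes all point to one, and a repeated measures model in a randomised study can carry a group-by-time term. Model terms are commonly left to an analysis plan, which is not at hand. This stands: a reader might infer that no arm comparison is planned, and the protocol does not support that. Two things remain. The protocol itself states the target of its significance rule, and that target is change over time. The comparative phrase in 9.1 speaks of estimates, covers patient-reported outcomes only, and is not linked to the test.

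**Sections 2.2 and 9.1 agree on method.** Section 2.2 also proposes to examine change over time. This is true, and it moves part of the problem rather than removing it: 2.2 sets an impact question and then names a means that cannot answer it, so the mismatch lies within 2.2 as well as in 9.1.

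**The protocol does not predict the same shift in both arms.** Section 1.2.1 describes decline in patients who wait with little or no training, which is closer to usual care, and section 1.2 gives the benefits of CABG without a time frame. A reader might infer that the protocol expects equal change whatever the allocation; it does not say so. The equal-shift figures illustrate the principle and are not a forecast.

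**The opening limit could be read as meant for feasibility only.** The sentence on the primary study parameter invites that reading. But the opening sentence lists the proposed endpoints separately from the feasibility measures, so the limit appears to cover the clinical endpoints too. It has to be reconciled with the close, not reinterpreted.

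**P-values on explorative outcomes are not in themselves an error, and labelling them so would be a lighter change.** That is fair as far as it goes. A label alone would still leave the threshold attached to change over time.

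**Conclusion.** The point holds as an internal contradiction in 9.1 together with a significance rule whose stated target does not answer the impact question. It does not extend to a claim that arms will not be compared, nor to a criticism of unstated model terms.

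Its size depends on how the rule is read and on assumed effects. A pooled time test would be significant in 28% of trials at an equal shift of 0.2 SD and in 93% at 0.5 SD with no treatment effect. A between-arm test would have about 41% power at a true difference of 0.5 SD, or 52% with baseline adjustment at r = 0.5. Under either reading the threshold fits poorly with outcomes that the protocol calls explorative and a study without a power calculation.

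The text should be corrected in the protocol, because an analysis plan cannot comply with both statements. The primary feasibility conclusions are unaffected.

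**What to change.** In Protocol section 9.1:

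1. Reconcile the opening sentence with the closing ones. State that feasibility and clinical endpoints are summarised descriptively by arm (mean and SD for continuous variables), and that exploratory between-arm estimates are added for the continuous secondary outcomes. The SDs by arm also serve the sample-size planning named in 2.2.
2. Delete the sentence that sets the 0.05 threshold.
3. State that, for each repeatedly measured continuous secondary outcome, the baseline-adjusted between-arm difference with its 95% confidence interval will be reported at the post-baseline times marked for it in Table 2, and labelled exploratory. Grip strength and body composition, for example, have no 30-day mark. Leave the blood values out of this sentence, because Table 1 places their second measurement after the intervention, whereas Table 2 marks it at 4 days postoperative and lists them under other outcomes.

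Model terms may stay with the analysis plan. The cost is two or three sentences and no new data. The price is giving up significance claims on secondary outcomes.
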